Study design	
The primary intervention study will be conducted using a parallel-group cluster non-randomized controlled superiority trial study design implemented in two phases. Additional mixed-methods operational research will take place throughout the intervention period.
 
Phase 1: parallel cluster randomized controlled study in 32 health facilities
 
The ePOCT+ tool will be introduced sequentially using in three implementation blocks of 10-12 (half intervention and half control) facilities. Each of the parallel cluster study (implementation block) will last for approximately four months, with the first month serving as a phase-in period. The aim is to compare the effect of using ePOCT+ with

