--	---

	
 
- Carbon footprint of the intervention or carbon-saving due to the intervention
 

Procedures and measurements	
Objective 1: Improve integrated management of sick children
 
In Phase 1, eligible HFs will be grouped into three implementation blocks of 10-12 health facilities (half intervention and half control). Randomization will not be done for reasons of feasibility and high chance of contamination if control and intervention facilities are mixed and in close proximity to each other as randomized. Therefore, boundaries between groups of intervention and control facilities will be delineated geographically.
 
Sick children will be enrolled throughout Phase 1, as new blocks of facilities are introduced every four months and control facilities are converted into intervention facilities. Children enrolled in intervention facilities will be managed using ePOCT+, with all data associated with the consultation being captured electronically. Children enrolled in control facilities will be assessed, diagnosed and treated as per routine protocols by clinicians. A similar but simplified tablet or PC application will also be used in control facilities to record only outcome measure related data using an electronic case report form.
 
Primary outcome measure: For measuring antibiotics prescribed at initial consultation, the treatment data recorded in the tablets or PCs by HWs throughout the study will be compared between intervention and control facilities, captured electronically in both facility types.
 
Secondary outcome measure: For assessing clinical cure at day 7, a simple questionnaire (asking if the child is still sick, was hospitalized secondarily, or died) will be administered to all caregivers by phone.
 
In Phase 2, all HFs will be using ePOCT+. Indicators monitored over time and space will be measured the same way as in Phase 1, except that clinical cure, secondary hospitalizations and deaths may not be collected or will be assessed through an automated phone call or SMS sent to caregivers using the same simple questionnaire (resource dependent).
 
Secondary analyses will be used to assess differences in the quality of the consultation made by HWs, including the rational use of antimicrobials (antibiotics and antimalarials). Two sources of data will be used and compared between intervention and control facilities:
 
 
- the final decision on referral, tests performed, final diagnoses retained and treatment prescribed will be recorded in the tablets or PCs by HWs at initial consultations and re-attendance visits.
 
- during a cross-sectional quality of care survey, observers in the consultation room will record key symptoms and signs assessed by HWs, diagnostic tests requested, final decision on referral, final diagnoses retained and treatment prescribed.
 
 
Objective 2: Improve the algorithm and adapt it to spatiotemporal variations
 
In Phase 2 of the study, the algorithm will be improved in terms of diagnostic and prognostic accuracy and adapted to local fluctuations in epidemiology, demography, geography and resource availability. Each potential modification will first be evaluated by the Rwandan clinical expert group for its clinical coherence, safety and potential benefit, and then applied to the retrospective data. If these analyses confirm a clinically relevant positive impact, the change in the algorithm will be implemented in all relevant locations/patient sub-groups and monitored based on the indicators relevant to the specific change in the algorithm collected throughout the study through the tablets.
 
Objective 3: Enhance M&E and supportive supervision
 
Patient-level data will also enhance M&E activities and supportive supervision of the HWs through the medAL-monitor/medAL-outbreak platform. Clinicians will use data generated from their own consultations to self-audit their clinical practices by monitoring quality of care indicators in the medAL-monitor dashboards and improve their skills in specific areas using the e-learning platform. Similarly, members of the DHMT will use medAL-monitor to identify and provide support to HFs in need of additional training and mentorship. In time, this enhanced ability to capacitate HWs and

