### Exclusion Criteria:

[figure not shown]
- Secondary and Tertiary HFs (district, provincial, and specialized referral hospitals).
- Private facilities (VCT clinics, medical clinics, dispensaries).

Primary health facilities which could not be geo-located and matched with the HMIS data to assess utilization.

According to these criteria, a total of 48 PHC facilities in the two selected districts qualify for inclusion in Phase 1 of the study, including 29 health centers and 19 health posts. Of these, 32 will be conveniently selected for the parallel RCT study. The remaining six facilities that see at least 19 children for IMCI services per week, as well as the remaining smaller HFs (for a total number of up to 67 facilities) will be added during the scale-up in Phase 2. The final number of facilities is budget dependent.

 <https://moh.gov.rw/index.php?id=547>

**Figure 9:** Spatial distribution of all public health facilities (left) and their IMCI utilization (right).

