Since the intervention takes place at the health provider level and their practices are influenced by the context of the health facility they are working in, randomization at health facility level rather than at HCW level or at individual patient level was chosen. The randomization of clusters (i.e. health facilities) will be performed on a 1:1 ratio. Thus, ePOCT+ will be provided to health workers (HWs) of 16 of the 32 selected primary health care facilities (intervention arm) in Rusizi and Nyamasheke districts, while the other 16 health facilities (HFs) will serve as controls (control arm). Sick children aged 1 day to 14 years (inclusive) will be managed in accordance with the study arm to which the HF they attend has been assigned. The comparator for Phase 1 will be routine care as currently implemented in Rwanda supplemented with equivalent clinical training given to the intervention arm. To assess the primary and secondary outcomes, final decision on referral, laboratory test results, diagnoses and treatments at initial consultation will be recorded by HCWs electronically in both arms (in the intervention arm integrated into the CDSA; in the control arm via a simple eCRF without any decision support); children will also be followed-up by a phone call or home visit to their caregiver at day 7 (range 6-14) to determine their clinical status. The study is considered as pragmatic since there are no major exclusion criteria to the population of interest, and the setting and organization of the health facilities remains mostly the same. The trial design is summarized below. Furthermore, in line with the pragmatic nature of the study, the design is adaptive, in that changes in the implementation across the three parallel cluster studies may be made based on monitoring data and feedback from the health facilities. These implementation changes (excluding significant adaptations to algorithm content) will be thoroughly documented and accounted for in comparisons across the three cluster studies.

PHASE 1

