3.2 Allocation of health facilities to study arms

The 32 health facilities to be included in the study will be selected from all eligible health facilities in the participating districts (Rusizi and Nyamasheke). Eligible health facilities include public health centers with at least 19 consultations with children between 2 months and 5 years of age per week. Cluster inclusion and exclusion criteria will first be applied to the full list of health facilities in the participating districts prior to selection of the 32 health facilities. Health facilities (or clusters) will be allocated (1:1), to using ePOCT+ (intervention) or routine care (control group). Due to the pragmatic nature of the study, randomization is not possible. Health facilities will be allocated first to one of the three implementation blocks using geographical considerations, and then split into study arms, also using geographical considerations. Similar sample size by study arm and by implementation group will be maintained as much as possible.

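### Contamination justifies contiguous areas but not non-random assignment of those areas to arms; no rule for that choice is given, so the arm is open to selection

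*Protocol*

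**What the plan says.** The protocol synopsis (Procedures and measurements) gives two reasons for not randomising: "Randomization will not be done for reasons of feasibility and high chance of contamination if control and intervention facilities are mixed" and near each other. It concludes that "boundaries between groups of intervention and control facilities will be delineated geographically". SAP 3.2 gives a different reason, "Due to the pragmatic nature of the study, randomization is not possible", and does not mention contamination. It places facilities first into one of three blocks by geography "and then split into study arms, also using geographical considerations", and aims for similar sample size by arm and block. Neither document says who decides which area of a block starts ePOCT+, when, or by what rule.

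The facilities are themselves a convenience sample: Protocol 5.2 says "32 will be conveniently selected for the parallel RCT study".

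Other text describes the trial as randomised. SAP 3.1 says "The randomization of clusters (i.e. health facilities) will be performed on a 1:1 ratio". The synopsis (Study design) labels Phase 1 a "parallel cluster randomized controlled study in 32 health facilities", and Protocol 13 also calls Phase 1 randomised.

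Both halves of a block are trained and given tablets (Protocol 8.1.4 and 8.1.6). Groups 1, 3 and 5 start ePOCT+ at once, while groups 2, 4 and 6 first have a four-month control period. SAP 5.4 plans to compare baseline data between arms in order to confirm that the lack of true randomisation caused no bias. SAP 6.1 adds imbalanced baseline characteristics to the model as fixed effects.

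**The concern.** Two decisions are run together. The first is whether facilities of the two arms are interspersed, and the contamination argument answers it. The second is which of two contiguous areas in a block becomes the intervention area, and the argument does not reach it. Within a block, the boundary is the same whichever side is intervention.

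Leaving the second decision without a rule matters because it fixes the contrast. Protocol 4.1 compares the primary outcome between the paired groups of a block, so an existing difference in prescribing between the two areas passes straight into the estimate. An area chosen because it is better staffed, more motivated or already prescribing less would show an apparent reduction.

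Area differences are plausible. Protocol Table 5 gives under-five fever of 33% in Rusizi and 14% in Nyamasheke, and acute respiratory infection of 14% and 5%. Protocol 1.2 reports antibiotic use of 49% for respiratory infection, 39% for fever and 10% for diarrhoea. The documents do not say how the areas map onto the districts, so this shows only that geography can carry prescribing differences.

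**Working it through.** **The plan's own figure.** Inputs from SAP 3.3: 35% against 26%, 80% power, two-sided alpha 0.05, 660 patients per cluster, ICC 0.025. Two proportions need 410 per arm. The design effect is 1 + (660 − 1) × 0.025 = 17.475. Then 410 × 17.475 / 660 = 10.86, rounded up to the stated 11 clusters per arm. These inputs can therefore be used for the size of the concern. With 16 clusters per arm the same assumptions give 92.6% power. A lot within each block changes neither facilities nor patients, so that figure is unaffected.

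**Size if the choice favoured low prescribing.**
- Between-facility variance: 0.025 × 0.35 × 0.65 = 0.00569, SD 0.0754 (7.5 points).
- Facilities per area: 32 / 6 = 5.33. SD of an area mean: 0.0754 / √5.33 = 0.0327 (3.3 points).
- SD of the difference between two areas: 0.0327 × √2 = 0.0462 (4.6 points).
- Expected absolute difference under normality: 0.798 × 0.0462 = 0.0369 (3.7 points).
- Relative to control: 0.0369 / 0.35 = 10.5%. Relative to the planned effect: 0.0369 / 0.09 = 41%.

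This is the expected spurious difference if the lower-prescribing area were picked in all three blocks. Against SAP 6.1's success criterion of 25% less prescribing, read as a point estimate: with control at 35%, the line is 0.75 × 35 = 26.25%. An intervention area already at 35 − 3.7 = 31.3% reaches it with a true reduction of 1 − 26.25 / 31.3, about 16%.

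**Size if the choice is unrelated to prescribing, or is drawn by lot.** Expected bias is zero. Chance imbalance averaged over three pairs has expected absolute size 0.798 × 0.0462 / √3 = 0.0213 (2.1 points).

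**What three lots can support.** There are 2³ = 8 allocations. The smallest exact p-value is 1/8 = 0.125 one-sided, or 2/8 = 0.25 two-sided. Six pairs would be needed to go below 0.05 two-sided (2/2⁶ = 0.031).

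**Whether the planned analysis can repair selection.**
- Groups 1, 3 and 5 have no control period, so the trial data hold no routine-care prescribing for them.
- SAP 5.4 lists facilities by district, patient volume, readiness score, age, sex, reasons for consultation and history of fever. Prior prescribing is not listed, and clinical signs and comorbidities are not systematically collected.
- The pre-intervention quality-of-care survey (Protocol 4.2.2) observes 25 consultations in each of 18 facilities. At 35%, one facility's proportion has standard error √(0.35 × 0.65 / 25) = 0.095, or 9.5 points, wider than the 7.5-point facility SD. The SAP does not name it as an adjustment variable.

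**The case against.** Contamination is not the only stated reason. Feasibility is named first in the synopsis, and the SAP cites pragmatism. Both stand as unexplained rather than refuted, although training and equipping both halves of a block makes a practical barrier to a draw hard to see.

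A reader might infer that contamination is identical whichever area gets ePOCT+. That holds for the boundary inside one block. It is not shown for blocks 2 and 3: blocks start in sequence and control areas convert, so a later control area might border areas already using ePOCT+. The layout figures are not shown, and separation of this kind is one possible meaning of the SAP's geographical criterion. For the same reason it cannot be said that choosing by hand gains nothing; the documents simply describe no gain.

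A reader might also infer that the study team picks arms knowing the facilities' prescribing. The documents do not say who picks or with what knowledge. The facility-level HMIS data in Protocol 5.2 are used to assess utilisation.

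The plan has safeguards: cluster-level baseline items and adjustment (SAP 5.4 and 6.1), a facility assessment in all facilities (Protocol 4.2.1), the pre-intervention survey, and within-facility comparisons of control with intervention periods in groups 2 and 4 (Protocol 4.1). These help, and the within-facility comparison does not rest on the contrast between areas. None supplies routine prescribing before ePOCT+ across the intervention facilities.

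Finally, the non-randomised design is openly declared in several places, and three lots improve it only modestly.

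**Conclusion.** The contamination argument supports contiguous areas and goes no further. With no rule stated for assigning areas, and no means in the planned analysis of reliably removing selection, the arm is open to a bias that a lot would take away in expectation.

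The 3.7 points are the result of choosing with perfect knowledge in every block, not an estimate of what will happen; if the geographic choice is unrelated to prescribing, the expected bias is already zero. The calculation uses the plan's ICC and 35% rate, normality and facility-level variation only. Correlation between facilities of one area, for which the documents give no figure, would raise both the 3.7 and the 2.1 points.

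A lot removes discretion, not imbalance: about 2.1 points of expected absolute imbalance remain, and eight allocations cannot carry a test at 0.05. It also leaves the convenience selection of facilities as it is. A reader might suppose that the SAP already cautions about inference from this allocation. It does not: SAP 5.4 claims that a baseline comparison will confirm no bias, which such a comparison cannot do.

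This is a cheap improvement that should be made. It does not show that the trial is biased.

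**What to change.** In SAP 3.2 and Protocol 4.1:

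- Draw two contiguous areas of similar size in each block and list their facilities.
- Where either assignment gives acceptable separation from areas already using ePOCT+, assign intervention and control by a documented lot before any facility is told its group.
- Where the layout does not permit this, state the geographic rule used, who applied it, when, and with what knowledge of baseline prescribing.
- Describe the result as area-level assignment of three pairs, saying which were drawn by lot. Reconcile the randomised wording in the synopsis (Study design), Protocol 5.2, Protocol 13 and SAP 3.1 with it.
- In SAP 5.4, replace the claim to confirm no bias with a statement that three pairs do not ensure balance (about 2.1 points of expected absolute imbalance under the plan's ICC) and cannot support a randomisation test at 0.05 (at most 8 allocations, smallest two-sided p 0.25).

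The cost is at most three lots and a few sentences. Facility numbers and power under the plan's own assumptions are unchanged. The team gives up its choice of which area starts.

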## 1 BACKGROUND AND RATIONALE

### 1.1 Management of sick children

Children are a well-recognized vulnerable population that still suffers from high rates of acute infectious diseases and preventable deaths due to inadequate clinical management at the PHC level. In PHC settings, health professionals rely on generic guidelines, such as the WHO IMCI booklet (WHO 2014A), while often lacking diagnostic tools, skills, and supportive supervision, which can lead to misdiagnoses and inappropriate prescription practices. This is especially true in the fragile health systems of sub-Saharan Africa, where under-five mortality is ten times that of high-income countries. Rwanda has made significant progress in reducing under-5 mortality, with recent mortality rate estimates (35 deaths per 1,000 live births) less than half those of sub-Saharan Africa (78 deaths per 1,000 live births) (World Bank 2018). Nonetheless, further progress is possible, with children still dying of preventable causes such as pneumonia, meningitis, malaria and acute respiratory infections according to a recent verbal autopsy study (Gupta et al. 2018).

The IMCI strategy, used in the PHC outpatient setting, with its integrative disease management approach, remains very relevant today. Yet its implementation has faced major challenges, largely related to format and content-related shortcomings (Rambaud-Althaus et al. 2017; Lange, Mwisongo, and Mæstad 2014; Baiden et al. 2011). For example, the IMCI booklet requires integrating information from about 20 pages during a consultation, which is a great challenge for HWs. Additionally, the IMCI algorithm is over-reliant on clinical signs and symptoms, which consume the majority of the consultation time and inherently lack diagnostic accuracy in children (Keitel et al. 2017; Rambaud-Althaus et al. 2015). Diagnostic POC tests that can help detect children with severe illness have not been incorporated into the IMCI algorithm.

Furthermore, static guidelines like IMCI tend to become rapidly outdated. With revision cycles of 5-10 years, they cannot keep up with new evidence and epidemiological changes. They tend to be too generic, in that only a single version exists for an entire country, while each region faces different types of diseases and levels of transmission. When an epidemic arises, such static and generic guidelines can even become dangerous: existing recommendations may become inapplicable with changing disease patterns. As a result, HWs may put standard guidelines aside to focus on the disease outbreak. For example, the risk of malaria deaths increased during the West African Ebola epidemic as HWs focused on Ebola case management (Walker et al. 2015).

### 1.2 Over-prescription of antimicrobials

In the absence of diagnostic tools, clear guidance, and supervision, it is challenging for HWs to confidently identify the minority of children with bacterial infections needing antibiotic treatment among the predominant cases of self-limiting diseases (Rambaud-Althaus et al. 2017). Thus, they tend to over-prescribe antibiotics - and sometimes also antimalarials - "to be on the safe side" (Hopkins et al. 2017, Fink et al. 2019). In fact, nine out of ten febrile children attending PHC facilities typically receive antibiotics, as compared to the one or two who actually need them ([name] et al. 2014). According to the most recent Demographic and Health Survey (DHS), approximately 49% of under 5 children with an acute respiratory infection (ARI), 39% with fever, and 10% with diarrhea received an antibiotic from a community health worker or a facility-based healthcare provider (DHS 2014-2015). Despite this high-volume and indiscriminate antibiotic treatment, mortality from childhood infections remains high. This is mainly because children with severe infections, which can be caused by viral, parasitic, or bacterial pathogens, are missed (Keitel et al. 2017). The over-reliance on antibiotics has also resulted in the neglect of other important supportive treatments for severe infections (e.g. oxygen therapy for viral bronchiolitis). Antibiotic over-treatment hinders the development of the natural, protective bacterial gut flora, which is an important immunological barrier (Benoun et al. 2016) and has been shown to be associated with cognitive neurological and behavioral development (Carlson et al. 2018, Loughman et al. 2020).

The tremendous overuse of antibiotics, especially in children at the PHC level where most patient encounters occur, contributes to the global spread of antibiotic resistance (AMR), which is a major public health threat, estimated to be responsible for up to 10 million deaths per year by 2050 (Holmes et al. 2016, Fink et al. 2019). According to the WHO, AMR is rising to dangerously high levels, especially in low-resource settings. Limited AMR surveillance data for Rwanda exists; however several studies conducted in tertiary and referral hospitals suggest widespread antimicrobial resistance among bacterial infections (Ntirenganya et al. 2015, Sutherland et al. 2019) with decreasing susceptibility trends for several antibiotic treatments between 2009 and 2013 (Carroll et al. 2016). Interestingly, a recent study among healthcare students in Rwanda found that the majority (up to 96%) demonstrated good knowledge of antibiotics, agreed that inappropriate use of antibiotics could lead to AMR, and that it was important for healthcare students to be knowledgeable about AMR. However, 38% did not believe that antibiotics were overused in Rwanda, approximately 20% believed that antibiotics are useful for viral infections like the flu, and 40% reported taking antibiotics without a prescription (Nisabwe et al. 2020). Antimicrobial stewardship among prescribers in outpatient settings, in combination with further education of healthcare professionals and the lay public are urgently needed to mitigate AMR.

